4.2. General Concomitant Medication and Supportive Care Guidelines.....	17
4.3. Duration of Therapy.....	17
4.4. Duration of Follow Up.....	18
4.5. Criteria for Removal from Study	18
4.6. Alternatives.....	18
4.7. Compensation	18
5. INVESTIGATIONAL AGENT/DEVICE/PROCEDURE INFORMATION	18
5.1. Investigational Agent/Device/Procedure	18
5.2. Availability	19
5.3. Agent Ordering	19
5.4. Agent Accountability	19
6. DOSING DELAYS/DOSE MODIFICATIONS	19
7. ADVERSE EVENTS AND REPORTING PROCEDURES	19
7.1. Potential Adverse Events	19
7.2. Adverse Event Reporting.....	21
8. CORRELATIVE/SPECIAL STUDIES	21
8.1. Laboratory Correlative Studies	21
9. STUDY CALENDAR	22
10. MEASUREMENT OF EFFECT	24
10.1. Anti-tumor Effect.....	24
10.2. Other Response Parameters	24
11. DATA REPORTING/REGULATORY CONSIDERATIONS.....	24
11.1. Monitoring Plan	24
11.2. Stopping Rules	25
11.3. Data Management	25

11.4. Confidentiality	25
12. STATISTICAL CONSIDERATIONS	25
12.1. Endpoints	25
12.2. Analysis Populations.....	26
12.3. Plan of Analysis	26
12.4. Sample Size.....	26
12.5. Interim analyses	27
REFERENCES.....	26

[figure not shown]
APPENDICES

- A. Participant Eligibility Checklist
- B. AE and SAE Reporting Guidelines
- C. Response Criteria in Mycosis Fungoides and Sezary Syndrome

PROTOCOL SYNOPSIS

TITLE	A Phase II Study of Non-myeloablative Allogeneic Transplantation Using Total Lymphoid Irradiation (TLI) and Antithymocyte Globulin (ATG) In Patients with Cutaneous T Cell Lymphoma
STUDY PHASE	II
INDICATION	Advanced Stage Cutaneous T Cell Lymphoma
PRIMARY OBJECTIVES	Clinical Response
SECONDARY OBJECTIVES	Engraftment and GVHD
HYPOTHESES	Graft versus Lymphoma effect provided by Non-myeloablative Allogeneic Transplantation will provide disease control
STUDY DESIGN	Single arm phase II
PRIMARY ENDPOINTS AND SECONDARY ENDPOINTS	Clinical response Incidence of GVHD, EFS, OS
SAMPLE SIZE BY TREATMENT GROUP	40 patients
SUMMARY OF SUBJECT ELIGIBILITY CRITERIA	Advanced stage cutaneous T cell lymphoma patients with HLA-matched related or unrelated donor
INVESTIGATIONAL PRODUCTS DOSAGE AND ADMINISTRATION	Total lymphoid irradiation (TLI) 800 cGy and anti-thymocyte immunoglobulin
CONTROL GROUP	Not applicable
PROCEDURES	Not applicable
STATISTICAL CONSIDERATIONS	Clinical response and incidence of GVHD will be reported as percentage. EFS and OS will be determined using Kaplan-Meier estimation.

SCHEMA

LIST OF ABBREVIATIONS AND DEFINITION OF TERMS

ADL	Activity of daily living
AE	Adverse event
BID	Twice daily
BSA	Body surface area
CBC	Complete blood count
CI	Confidence interval
CRF	Case report/Record form
CR	Complete response
CTCAE	Common Terminology Criteria for Adverse Events
DLT	Dose Limiting Toxicity
DSMC	Data Safety Monitoring Committee
ECG	Electrocardiogram
EFS	Event Free Survival
GVHD	Graft versus Host Disease
Hgb	Hemoglobin
HIV	Human Immunodeficiency Virus
IRB	Institutional Review Board
IV	Intravenous
OS	Overall survival
PLT	Platelet
PD	Progressive disease
PFS	Progression free survival
PR	Partial response
QD	Once daily
RR	Response rate
SAE	Serious adverse event
SD	Stable disease
TSEBT	Total skin electron beam therapy
TTP	Time to progression
UNK	Unknown
WBC	White blood cell

1. OBJECTIVES

1.1 Primary Objectives

To evaluate the graft versus lymphoma effect by monitoring rate of clinical response, event-free and overall survival.

1.2 Secondary Objectives

To evaluate the incidence and extent of acute and chronic GVHD and time to engraftment.

2. BACKGROUND

2.1 Study Disease

Mycosis Fungoides/Sezary Syndrome

MF is a mature T cell lymphoma that arises primarily from the skin. It is the major subtype of cutaneous T cell lymphoma (CTCL). Patients usually present initially with patch, plaque, tumor or erythrodermic involvement of their skin. MF has a long natural history (2). Many patients have non-specific skin manifestations for several years before a diagnosis is made. Although the initial lesions are usually limited skin patches or plaque, generalized plaques involving large body surface area and tumor lesions are common by the time patients seek medical attention. Extra-cutaneous dissemination may occur to lymph nodes, liver, spleen, lungs and blood (Sezary cells). SS is a leukemic form of MF in which patients have significant blood involvement with Sezary cells and diffuse erythroderma (3).

After the diagnosis is established, appropriate staging is important. Initial staging should include comprehensive skin examination, peripheral blood evaluation for Sezary cells, and appropriate imaging such as CT scan. The International Society for Cutaneous Lymphomas (ISCL) and the Cutaneous Lymphoma Task Force of the EORTC has recently published a revised TNM staging for MF/SS (4). Several large studies have shown that overall clinical stage determines long-term outcome. Patients with limited stage IA disease have a very favorable outcome with life expectancy comparable to matched control population. Patients with IB/IIA disease have a median survival of 11-12 years after diagnosis, with fewer than 20% experiencing progression to higher stage. However, stage IIB/III disease carried a worse outcome with median survival of 4-5 years and higher chance to have large cell transformation. Patients with stage IV disease have the worst, <2 year median survival (Figure 1) (2).

[figure not shown]

Figure 1 Actuarial overall survival of 525 patients at Stanford with MF/SS according to TNM stage at diagnosis.

Therapy for Mycosis Fungoides/Sezary Syndrome

Choosing appropriate treatment for individual patients is not easy. The most important consideration is the T (tumor) classification and overall clinical stage, with specific concerns for large cell transformation, acuity or severity of associated symptoms, and potential treatment related toxicities (5). In general, step-wise approach with first skin-directed therapy, then mild biological systemic therapy, and then systemic chemotherapy is the current strategy. Skin-directed therapies should be the first step to control skin lesions, which include topical steroids, topical nitrogen mustard, topical retinoids and phototherapy. Narrow-band UVB and Psoralen plus UVA are highly effective for thicker plaques. Total skin electron beam therapy, considered the most intensive skin-directed therapy, is reserved for patients with extensive generalized disease and severe skin symptoms (6). While clinical response is greater with more intensive skin-directed therapies, no improved progression free or overall survival has been shown.

For patients with refractory disease to skin-directed therapies or with advanced stage of MF (IIB-IV) and Sezary syndrome, systemic treatments should be included in the primary therapy strategy, with or without skin-directed treatments. The first category of systemic therapy is mild immunomodulating agents (biologics), such as systemic retinoids (bexarotene) (7), interferons (8,9), low dose methotrexate and newer reagents, histone deacetylase inhibitors (10), and denileukin diftitox (11). While these treatments have a slow time to response and generally provide partial response rates no greater than 50%, their lack of cumulative toxicity allows them to be used as maintenance treatment for long periods. Extracorporeal photopheresis (ECP) has been used as monotherapy or in combination with other systemic therapy and has been shown to be a very effective treatment, especially for disease control of SS (12). The next category of systemic therapy is more traditional cytotoxic chemotherapy. The most common reagents are liposomal doxorubicin, gemcitabine, chlorambucil and high dose methotrexate. Pegylated liposomal doxorubicin is effective as a single agent. In a prospective study, every 4 week infusions gave an overall response rate of 84% with 42% of the patients achieving complete response (13). However, these responses are usually short-lived and patients move from one agent to another agent, then proceed to combination chemotherapies, and eventually progress after multiple therapies.

Treatment with Hematopoietic Stem Cell Transplantation

Emerging data on allogeneic HSCT, particularly using non-myeloablative conditioning, suggest the existence of a graft-versus-T cell lymphoma effect. Allogeneic transplant should be considered in patients with advanced disease who fail to respond to all primary therapies or do not have durable response with salvage treatments.

Recently, we have performed a meta-analysis of studies treating MF/SS patients with HSCT in an attempt to understand its utility. In this analysis, 15 published reports with a total of 38 cases and 5 unpublished cases were included (14-28). Twenty three cases had high dose therapy followed by autologous HSCT and twenty cases had allogeneic transplant. The median age was relatively young of 42 years with an equal male/female distribution. All but one case had advanced stage (\geq IIB) disease at time of transplant. The median follow-up was 21 and 29 months for autologous and allogeneic transplant group, respectively. For autologous group, 12 cases received total body irradiation (TBI) and chemotherapy and 11 cases had only high dose chemotherapy. For allogeneic group, half of them received myeloablative preparative regimen with TBI plus chemotherapy; and the other half had non-myeloablative preparative regimen. As a whole group, the allogeneic transplant had a significantly longer event-free survival (EFS) than the autologous HSCT (Figure 2). In the autologous transplant group, 19 of 23 cases progressed/relapsed after transplant with median time to progression of 3 months. In contrast, only 5 of 20 cases progressed/relapsed with median time to progression not reached in allogeneic group.

The overall survival (OS) was also longer in allogeneic group than in autologous group (Figure 3). The estimated OS was 85% vs 65% at 1 year, 79% vs 56% at 2 year and 79% vs 36% at 5 year for the two groups. One hundred day post transplant mortality was 5% and 13% in allogeneic and autologous groups respectively. One year mortality was 15% and 35% for the two groups. While progressive disease caused 11 deaths in autologous group, none of the death in allogeneic cases was due to disease progression. The most interesting finding was that there was no difference in clinical outcome between the cases receiving myeloablative regimen and the cases having non-myeloablative approach in the allogeneic group.

[figure not shown]

Figure 2 Post transplant event-free survival of MF/SS patients according to the type of transplant ($p < 0.0005$).

[figure not shown]

Figure 3 Post transplant overall survival (OS) of MF/SS patients according to the type of transplant ($p = 0.028$).

Although this is a very small sample size with many limitations, this meta-analysis suggests several important points related to the use of HSCT to manage MF/SS:

- 1) High dose therapy with either TBI or chemotherapy has not provided significant clinical benefit given the extremely short time to progression (3 months) in autologous transplant experience.

- 2) A significant fraction of cases remained in progression free status after allogeneic transplant, suggesting an effective graft-versus-MF/SS effect.
- 3) Non-myeloablative approach for allogeneic transplant is a reasonable option, especially given that the median age at diagnosis is 55-60 years and compromised skin is frequently present in these patients, which increases the risk of infection. Therefore, we propose a clinical study with allogeneic HSCT using a unique non-myeloablative preparative regimen, TLI/ATG, to treat advanced MF/SS.

2.2 Investigational Agent/Device/Procedure

Total lymphoid irradiation (TLI)/antithymocyte globulin (ATG) preparative regimen

One of the concerns using allogeneic HSCT is the toxicity related to transplantation process. While graft-versus-lymphoma is highly desired for a long-term disease control, the mortality and morbidity from preparative regimen, infections and graft versus host disease (GVHD) makes allogeneic transplant difficult to apply to patients with indolent lymphoma. To overcome this, preparative regimens of non-myeloablative radiotherapy, chemotherapy, or both to decrease early toxicity have been used (29-32). However, acute GVHD remains a major problem after non-myeloablative transplantation and is responsible for approximately 50 percent of the deaths that are not due to a relapse of the neoplasm (31-33).

A new approach to the prevention of acute GVHD takes advantage of the immune system's regulatory T cells. Two types of regulatory T (Treg) cells in mice, natural killer T cells and CD4+CD25+ T cells, can prevent acute GVHD (34-37). These Treg cells inhibit the proliferation of and cytokine secretion by CD4+ and CD8+ donor T cells that injure the intestines, liver, and skin in acute GVHD (34,37). Nevertheless, the direct tumor-killing activity mediated by donor CD8+ T cells remains unaffected (35). Thus, Treg cells can separate GVHD from the antitumor activity of the graft. Regulatory natural killer T cells of either donor or host origin have the unique capacity to prevent acute GVHD by secreting interleukin-4 (36-38). In a mice models, after repeated treatment with low-dose irradiation targeted to the spleen, thymus, and lymph nodes (total lymphoid irradiation, TLI), the proportion of these cells progressively increases until ultimately they constitute the majority of T cells in the spleen and bone marrow (37, 38). In preclinical studies, murine recipients of allogeneic bone marrow that underwent conditioning with anti-T-cell antibodies and TLI were fully protected from GVHD, whereas mice that underwent conditioning with anti-T-cell antibodies and a single dose of total-body irradiation were not protected (37, 38). Studies of the pattern of cytokine secretion by donor T cells in protected hosts showed a polarization toward a pattern of type 2 helper T (Th2) cells, with increased secretion of interleukin-4 (38). The Th2 cells assist B cells to produce antibodies and reduce the inflammation promoted by type 1 helper T cells.

To apply this novel non-myeloablative regimen of TLI and ATG for allogeneic HSCT, a clinical trial has been conducted in patients with hematological malignancies other than myelodysplasia or myeloproliferative disorders since December 2001. Analysis of the first 37 patients (last patient enrolled in 2004), 19 of whom had NHL, appeared in the New England Journal of Medicine (39). The regimen consisted of 800 cGy in 10 fractions over 11 days with ATG administered at 1.5 mg/kg/d from day -11 to -7. The median age was 56 (28-65) years and 35% had failed prior autologous HSCT. Multi-lineage chimerism was achieved within 56 days and sustained in 31 of 37 patients. Of the 6 who lost their grafts, 4 were in the setting of progressive disease. Minimal neutropenia was observed and more than half of patients did not require hospitalization. Remarkably and in agreement with the preclinical studies, 35 of 37 patients developed no acute GVHD. Among the 18 patients in partial remission at transplant, 10 achieved complete remission, strongly suggestive of retained graft versus tumor effect. Among the 17 patients in complete remission at transplant, 11 continued to be disease-free at 1.5 years. Transplant-related mortality in this study was just 5% at 180 days. To date, 4 deaths due to disease progression and 4 deaths related to the procedure have been recorded. Overall, these results indicate that preparation with TLI/ATG and allogeneic HSCT is well tolerated, associated with prompt multi-lineage engraftment and a markedly low incidence of acute GVHD, with a strong suggestion of retained graft versus tumor effect.

Update on experience in B cell lymphoma patients

Since the initial report, we continue to accumulate the experience using this novel non-myeloablative preparative regimen. To date, we have performed allogeneic HSCT using TLI/ATG preparative regimen in 111 patients. Sixty four of the patients had malignant lymphoma. The majority of the patients (83%) achieved full donor chimerism (> 95% donor cells) and the transplant was well tolerated.

The one-year non-relapse mortality was 2% for patients receiving HLA-matched sibling donor graft and 8% for patients having HLA-matched unrelated donor graft. Acute GVHD only occurred in 4% of the patients, while the incidence of chronic GVHD is estimated to be around 35-45% at 2 years. For patients with lymphoma, the disease control was significantly better in patients who responded to salvage chemotherapy prior to transplantation than those who had refractory disease (Figure 4). One possibility is that graft-versus-lymphoma effect is a slow process after non-myeloablative allogeneic transplant and is unable to control high tumor burden or fast growing tumor in time. Therefore, we propose in this project to use non-myeloablative allogeneic HSCT in MF/SS patients after they achieve some degree of disease control with salvage therapy. One important observation was that patients who failed to achieve full donor chimerism had significant chance to relapse after transplant.

[figure not shown]

Figure 4 Actuarial event-free survival among patients with lymphoid malignancies (non-skin) stratified by disease status at transplant (N=64).

2.3 Rationale

Mycosis Fungoides (MF) and its leukemic variant, Sezary Syndrome (SS) is the most common type of cutaneous non-Hodgkin's lymphoma (NHL) in North America. Though most of the patients have an indolent course with median survival of 12-15 years, those with advanced diseases have a survival of 1-3 years after diagnosis, and there is no curative therapy (1). While localized skin treatment, novel biological therapies such as histone deacetylase inhibitors, or systemic chemotherapy can temperately control the diseases, none of these provide a long-term remission. Graft-versus-lymphoma effects after allogeneic hematopoietic stem cell transplantation (HSCT) have been demonstrated to provide a long-term disease control in B cell lymphoma, including low-grade B cell lymphoma and chronic lymphocytic leukemia. We propose a clinical trial using non-myeloablative allogeneic HSCT to treat patients with advanced stage MF/SS. The rationale is that graft-versus-lymphoma provided by this non-myeloablative approach will result in a clinical response and a prolonged progression free survival in these patients. The patient population enrolled in this clinical trial will be those with MF/SS who still have persistent or progressive disease after being treated with multiple lines of local and systemic therapies. When MF/SS reached this stage of their disease, the conventional chemotherapies will no longer provide any clinical benefit. Therefore, we proposed using this low toxicity allogeneic HSCT protocol to these patients.

2.4 Correlative Studies Background

2.4.1 Donor Cell Chimerism: The standard definition for full engraftment is that the percentage of donor cells in CD3 population rises above 95%. While most of our patients (83%) having undergone TLI/ATG preparative regimen reached full donor chimerism, the timing to achieving full chimerism varied significantly. It is of great interest to determine whether the full donor chimerism correlates to clinical response. In addition, donor chimerism of different cell populations may also have a significant impact on

clinical outcome. We will attempt to correlate the kinetics of donor chimerism of different cell populations to tumor response, disease progression, and GVHD. One prediction is that rising donor CD3/CD4/CD8 cells correlate to tumor response.

2.4.2 Profile of Grafting Immune Cells: To assess the T cells immune profile, intracellular cytokines with monoclonal antibodies against IL-2, IFN- γ (Th1 pattern), IL-4 and IL-10 (Th2 pattern) will be assayed. In mouse models, TLI/ATG polarized T cells to a Th2 pattern, which has been thought to be critical for graft-versus-tumor effect. Therefore, it is of great interest to see whether this Th2 polarization can be recapitulated in humans and whether Th2 polarization may affect tumor response. In the case of MF/SS, it is more complicated as most of the tumor T cells express Th2 phenotype (44). Whether this will facilitate or hamper the graft-versus-tumor effect by the donor T cells is unknown.

2.4.3 Donor T Cell Trafficking: Engrafted donor T cells have to be in close contact with the tumor cells to help antigen-presenting cells (APC) to cross-prime cytotoxic CD8 T cells. Recently, chemokine receptors, CCR4, CCR10 and cutaneous lymphocyte antigen (CLA) have been shown to play a critical role in mediating CD4 T cell trafficking to skin in both mice and humans (45-49). We will first test whether the peripheral blood T cells express these skin homing receptors by using multi-color flow cytometry. In addition, CCR7 has been shown to mediate the homing of T or B lymphocytes to lymph nodes (50), which is an essential step after T cells being primed in the tumor sites. In addition, examining the skin tumor site after transplant will be extremely informative to determine whether donor T cells reach the tumor sites.

2.4.4 Regulatory T cell (Treg): Treg cells have been implicated in many important aspects of allogeneic transplant, such as modulating graft-versus-tumor effect and damping GVHD. Recent studies have also pointed a role for Treg in the progression of MF/SS and in immunomodulation in the skin (52,53). Therefore, monitoring the number and function of Treg will be performed. We will monitor the number of Treg in blood and their function using a mixed-lymphocyte-reaction (MLR) inhibition assay (39).

We will specifically monitor the number and function of Treg cells in patients who undergo ECP or TSEBT. The status of Treg cells in these patients becomes even more interesting because these treatments have been proposed to mediate their therapeutic effects via modulating Treg (54).

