4.1.6 Engraftment and Disease Status Monitoring

- s) Patients will be followed in the ITA for signs of infection or GVHD. Monitoring for engraftment and infection will be according to current standard of care of Stanford BMT program.
- t) Chimerism: Microsatellite analysis (VNTR) of CD3, CD19, CD15, and CD56 peripheral blood cell subsets will be performed on days +28 (\pm 5 days), +56 (\pm 5 days), +90 (\pm 14 days), +180 (\pm 14 days), +270 (\pm 14 days), and yearly (\pm 4 weeks) to evaluate the degree of donor hematopoietic cell engraftment (donor chimerism), and on bone marrow on day +90 (\pm 14 days), and yearly per physician's discretion.
- u) Clinical response will be determined at 3, 6, 9, 12, 18, 24 months or until relapse or progression after transplant. The disease status and clinical response will be scored on a rigorous and multifactorial approach described before (41, appendix). This approach takes tumor burden in skin, lymph nodes and blood into consideration. To achieve this, patients will be evaluated at Cutaneous Lymphoma Clinic before transplant and at specified time points after transplant.

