9. STUDY CALENDAR

	BS	Post-Transplant Day							
		±5 days	±5 days	±10 days	± 2 wks	± 2 wks	± 2 wks	± 4 wks	± 4 wks
		d+30	d+60	d+90	d+180	d+270	d+365	d+540	d+730
Informed Consent	X								
Path Review	X								
H&P/KPS	X								
PFT	X								
Echo	X								
CBC with diff	X								
Chemistry: BMT I	X								
HLA confirmed	X								
BMT Panel (serologies)	X								
CXR	X								
EKG	X								
STR subsets: PB		X	X	X	X	X	X**		X
BM bx/asp**	X			X			X		X
Research Samples		X	X	X	X				
Skin Biopsy	X			X					
Flowcytometry** (SS only)		X		X	X	X	X	X	X
Disease Status/Response**	X			X		X	X	X	X
GVHD assessment	X	X	X	X	X	X	X		X

** Per Attending Physician's discretion

Correlative Study Calendar

	Donor Chimerism	Chemokine Receptor Profile	Th1/Th2 Phenotype	Treg Cell Quantity	Treg Cell Function	Skin Biopsy Pathology	Skin Biopsy T Cell Trafficking	Derm Clinical Assessment	Bone Marrow Biopsy	CTL Assay	Tumor Cell Banking
Pre TSEBT		X		X		X		X	X	X	Sezary only
Pre TLI/ATG		X		X		X	First 5 pt	X			
Pre Infusion		X		X							
+ 30 day	X	X	X	X	First 5 pt			X			
+ 60 day	X	X	X	X				X			
+ 90 day	X	X	X	X	First 5 pt	X	First 5 pt	X	X	X	
+ 180 day	X	X	X	X	First 5 pt		First 5 pt	X	X	X	
+ 270 day	X	X	X	X				X			
+ 1 year	X	X	X	X	First 5 pt		First 5 pt	X	X	X	
+ 2 year	X							X	X		
Cell Product		X	X	X							
Pre ECP		X	X	X							
Post ECP		X	X	X							
Disease Regression						X		X			
Disease Progression						X		X			
Sample		Up to 5 GGT			5 mm punch	5 mm punch		Routine	2 GTT for effector	2 GTT	
Site	HLA Lab	HIMC	CTF	CTF	CTF	Path	CTF	Cut Lym Clinic		HIMC	HIMC
Assay	Chimerism: CD3, CD19, CD56, CD15	Skin: CCR4, CCR10, CLA; LN: CCR7	Th1: IL-2, IFN γ ; Th2: IL-4, IL-10	FoxP3 positive	Inhibition of MLR	Monitoring Residual Disease	Lymphocyte Donor Chimerism, Chemokine receptor		FAM-VAD Assay	Use as Target Cell for CTL	

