12.3.6 Methods for Correlative Studies

Analyses of the correlation of response and other outcomes with measures of chimerism and other markers will be done with standard methods, including fixed and time-varying Proportional Hazards models and graphical methods. Given the small sample size, we do not expect to have power to do more than explore such correlations.

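### In patients with circulating tumour cells, CD3 donor chimerism partly measures tumour burden, so its exploratory correlation with response leans towards the predicted result even with no graft effect

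*Combined protocol and SAP*

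**What the plan says.** **The measure.** Section 2.4.1 states "The standard definition for full engraftment is that the percentage of donor cells in CD3 population rises above 95" per cent. Section 4.1.6 sets the assay: "Microsatellite analysis (VNTR) of CD3, CD19, CD15, and CD56 peripheral blood cell subsets will be performed on days +28", with later visits to day +270 and then yearly. The correlative calendar in Section 9 lists the same four subsets: "Chimerism: CD3, CD19, CD56, CD15".

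**The question asked of it.** Section 2.4.1 says "It is of great interest to determine whether the full donor chimerism correlates to clinical response" and adds a direction: "One prediction is that rising donor CD3/CD4/CD8 cells correlate to tumor response". Section 12.3.6 gives the method: "Analyses of the correlation of response and other outcomes with measures of chimerism and other markers will be done with standard methods". It names fixed and time-varying proportional hazards models and graphical methods, and says the small sample allows no more than exploration.

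**The tumour.** Section 2.1 says "MF is a mature T cell lymphoma that arises primarily from the skin" and "SS is a leukemic form of MF in which patients have significant blood involvement with Sezary cells and diffuse erythroderma".

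**The outcome.** Appendix C builds the global response from skin, nodes, blood and viscera. Blood CR is B0, and blood relapse after CR is a return to B1 or higher.

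**What is not said.** No section removes tumour cells from the CD3 fraction, adjusts for their number, or analyses blood-involved patients separately. Section 4.1.7 monitors Sezary cells by flow cytometry in SS patients but does not link the counts to the chimerism analysis.

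**The concern.** Donor CD3 chimerism is a proportion whose denominator holds every CD3 cell in the sample. In a patient with circulating disease, that includes host tumour T cells. The same cells feed the blood component of response. Clearing them by any route, such as the optional photopheresis from about day +30 in Section 4.1.7, raises measured chimerism and improves response together. If they persist, both get worse. A time-varying hazards model has the same problem, because a fall in donor CD3 % may be the first sign of progression in blood.

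Evaluating a graft-versus-lymphoma effect is the primary objective in Section 1.1. In a single-arm trial, a correlation between engraftment and response is one of the few pieces of mechanistic evidence available. The risk is that a partly built-in association is read as support for that mechanism.

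There are two related gaps. The prediction names donor CD4 and CD8 cells, which neither Section 4.1.6 nor the calendar types. And Section 2.4.2 notes that most tumour T cells in MF/SS have a Th2 phenotype, yet no step separates them from donor cells in the Th1/Th2 readout.

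**Working it through.** The plan gives no figure for this correlation. Its one precision figure, 58% to 88% for 27/36 in Section 12.4.2, concerns PFS. It reproduces as an exact interval (57.8% to 87.9%) and plays no part here.

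**Step 1: the threshold.** Let D be donor T cells, H normal host T cells and S host tumour T cells, all per uL and all CD3-positive.

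Measured donor CD3 % = D / (D + H + S)

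In the case most favourable to engraftment, H = 0. Then exceeding 95% requires S < D × 0.05/0.95 = D/19:

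- D = 300: S < 15.8
- D = 500: S < 26.3
- D = 1,000: S < 52.6

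The values of D are assumed, because the documents give no post-transplant counts. For scale, Appendix C uses more than 1,000 neoplastic cells/uL as a loss-of-response count in blood. At S = 1,000, a fully engrafted patient measures 500/1,500 = 33% or 1,000/2,000 = 50% for D = 500 or 1,000. Passing 95% would need more than 19 × 1,000 = 19,000 donor T cells/uL.

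**Step 2: what this does to the correlation when there is no graft effect.** Inputs: n = 40 (Section 12.4.1); 83% true full chimerism (Section 2.4.1), independent of response; 60% response and an SS share of 30% or 50% (both assumed). An SS patient above the limit is scored as not fully chimeric. The expected observed proportion is then

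0.83 × (1 − SS share × proportion of SS patients above the limit),

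calculated separately in responders and non-responders. If all SS non-responders and no SS responders are above the limit, it is 83% in responders. In non-responders it is 0.83 × 0.70 = 58% at 30% SS, or 0.83 × 0.50 = 41.5% at 50% SS.

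The table shows the share of 20,000 simulated trials with two-sided Fisher p < 0.05:

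| SS non-responders above limit | SS responders above limit | 30% SS | 50% SS |
|---|---|---|---|
| 100% | 0% | 34% | 72% |
| 100% | 40% | 12% | 26% |
| 50% | 0% | 11% | 25% |
| 70% | 40% | 6% | 9% |
| 25% | 0% | 5% | 8% |

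With no SS patients the figure is 2.5%. If half of each group is above the limit it is about 3%. The bias therefore comes from the difference between the groups, not from the presence of tumour cells alone.

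**Step 3: a second model, with cell counts simulated.** Assumptions: 50% response; median 500 non-tumour T cells/uL; median 250 or 1,000 tumour cells/uL in SS non-responders; blood cleared in 60% of SS responders. Rejection was 9–11% at 25% SS, 17–21% at 40% and 36–42% at 60%. With tumour cells removed from the denominator at 40% SS, full chimerism was 83% in both groups and rejection was 2.4%.

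**The case against.** **The analysis is exploratory.** Section 12.3.6 says so, and chimerism correlation is not among the endpoints in Section 12.1 or the stopping rules in Section 11.2. This stands and limits the consequence to interpretation. It excuses low power, but not an association that the measure itself helps to create.

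**The large error rates are not a property of this plan.** A reader might infer that 34% or 72% is the trial's false-positive rate. The documents do not support that. They name no Fisher test and no significance level, and give no SS share. Those two values also need every SS non-responder, and no SS responder, to exceed the limit. Appendix C allows otherwise: a global PR is possible with skin CR while blood is short of CR, a blood PR needs only a fall of more than 50%, and a patient may fail on skin, nodes or viscera with blood at B0.

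**The premise about CD3 is not in the documents.** They do not say that Sezary cells keep surface CD3 or enter the CD3 selection. This stands as an assumption, and partial loss shrinks the effect.

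**The plan already holds part of the remedy.** Section 2.4.1 intends to look at chimerism in different cell populations, and CD19, CD15 and CD56 are typed. Section 2.4.2 itself concedes that Th2 is harder to read in this disease. But nothing says which subset carries the graft interpretation when blood is involved.

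**The 95% rule was not imported.** A reader might suppose that the CD3 threshold was carried over from the group's earlier patients. Section 2.4.1 presents it as the standard definition, and the earlier experience in Section 2.2 gives more than 95% donor cells without naming CD3. The difficulty lies in applying the definition to a T-cell tumour.

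**Conclusion.** The point holds for patients with blood involvement, mainly those with SS. There, the CD3 chimerism–response correlation is biased towards the predicted positive direction without any graft effect, provided that more non-responders than responders keep circulating tumour cells above about D/19. The scoring of blood within response makes that likely. The D/19 limit rests only on tumour cells being CD3-positive.

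The size is not determined by the documents. Across the illustrations in the table, a false association arises in about 5% to 34% of trials at 30% SS and about 8–9% to 72% at 50% SS, with the top values as upper bounds.

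A reader might go further and conclude that the efficacy result is compromised. It is not: the primary endpoint is PFS at 180 days, and chimerism does not enter it. What is affected is how far the correlative data can support a graft-versus-lymphoma mechanism.

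**What to change.** Amend Sections 2.4.1 and 12.3.6 before these data are analysed:

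1. In patients with blood involvement, make CD15, CD19 and CD56 chimerism the main graft measure, and state that CD3 chimerism there will not be read as evidence of graft effect.
2. Report the CD3 correlation separately for patients with and without blood involvement at baseline. Do not restrict it to draws at B0: blood CR is B0, so that would select on part of the outcome.
3. As sensitivity analyses, correlate CD3 chimerism with skin and nodal response only and, where same-visit flow exists, recompute it with Sezary cells removed from the host CD3 fraction. The Section 9 calendar makes flow SS-only and discretionary, with none at day +60, so this recomputation will cover only some draws.
4. Restate the prediction as CD3 only, since CD4 and CD8 are not typed.
5. Interpret Th1/Th2 results separately in blood-involved patients.

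The cost is mainly analysis-plan text, because the non-T subsets are already scheduled at the same draws. The downsides are smaller subgroups, a weaker apparent correlation, and the fact that non-T subsets reflect T-cell engraftment only indirectly.
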